10.4.8. Data Quality Assurance

Data Quality Assurance/Quality Control

Quality tolerance limits (QTLs) will be pre-defined to identify systematic issues that can impact participant safety and/or reliability of study results. These pre-defined parameters will be monitored during the study and important deviations from the QTLs and remedial actions taken will be summarized in the clinical study report.

Steps to be taken to ensure the accuracy and reliability of data include the selection of qualified investigators and appropriate study sites, review of protocol procedures with the investigator and study-site personnel before the study, and periodic monitoring visits by the sponsor. Written instructions will be provided for collection, handling, storage, and shipment of samples.

Guidelines for eCRF completion will be provided and reviewed with study-site personnel before the start of the study.

The sponsor will review eCRF for accuracy and completeness during monitoring visits and after transmission to the sponsor; any discrepancies will be resolved with the investigator or designee, as appropriate. After upload of the data into the study database they will be verified for accuracy and consistency with the data sources.

10.4.9. Case Report Form Completion

Case report forms are prepared and provided by the sponsor for each participant in electronic format. All data relating to the study must be recorded in eCRF. All eCRF entries, corrections, and alterations must be made by the investigator or authorized study-site personnel. The investigator must verify that all data entries in the eCRF are accurate and correct.

The study data will be transcribed by study-site personnel from the source documents onto an eCRF, if applicable. Study-specific data will be transmitted in a secure manner to the sponsor.

Worksheets may be used for the capture of some data to facilitate completion of the eCRF. Any such worksheets will become part of the participant's source documents. Data must be entered into the eCRF in English. The eCRF must be completed as soon as possible after a participant visit and the forms should be available for review at the next scheduled monitoring visit.

All participative measurements (eg, pain scale information or other questionnaires) will be completed by the same individual who made the initial baseline determinations whenever possible.

If necessary, queries will be generated in the eDC tool. If corrections to an eCRF are needed after the initial entry into the eCRF, this can be done in either of the following ways:

- Investigator and study-site personnel can make corrections in the eDC tool at their own initiative or as a response to an auto query (generated by the eDC tool).
- Sponsor or sponsor delegate can generate a query for resolution by the investigator and study-site personnel.

10.4.10. Source Documents

At a minimum, source documents consistent in the type and level of detail with that commonly recorded at the study site as a basis for standard medical care must be available for the following: participant identification, eligibility, and study identification; study discussion and date of signed informed consent; dates of visits; results of safety and efficacy parameters as required by the protocol; record of all adverse events and follow-up of adverse events; concomitant medication; intervention receipt/dispensing/return records; study intervention administration information; and

date of study completion and reason for early discontinuation of study intervention or withdrawal from the study, if applicable.

The author of an entry in the source documents should be identifiable.

Specific details required as source data for the study and source data collection methods will be reviewed with the investigator before the study and will be described in the monitoring guidelines (or other equivalent document).

The following data may be recorded directly into the eCRF and may be considered source data:

- Race
- History of all nicotine use, eg, cigarettes (including e-cigarettes or the equivalent of e-cigarettes), cigars, chewing tobacco, patch, gum
- Blood pressure and pulse/heart rate
- Height and weight
- Details of physical examination
- Investigator-completed scales and assessments

The minimum source documentation requirements for Section 5.1, Inclusion Criteria and Section 5.2, Exclusion Criteria that specify a need for documented medical history may include:

- Referral letter from treating physician
- Complete history of medical notes at the site
- Discharge summaries
- Hospital admission records

Inclusion and exclusion criteria not requiring documented medical history must be verified at a minimum by participant interview or other protocol required assessment (eg, physical examination, laboratory assessment) and documented in the source documents.

An eSource system may be utilized, which contains data traditionally maintained in a hospital or clinic record to document medical care (eg, electronic source documents) as well as the clinical study-specific data fields as determined by the protocol. This data is electronically extracted for use by the sponsor. If eSource is utilized, references made to the eCRF in the protocol include the eSource system but information collected through eSource may not be limited to that found in the eCRF.

10.4.11. Monitoring

The sponsor will use a combination of monitoring techniques, ie central, remote, and/or on-site monitoring to monitor this study.

The sponsor will conduct monitoring activities as frequently as necessary. The first post-initiation visit will be made as soon as feasible. At these visits, the monitor will compare the data entered into the eCRF with the source documents (eg, hospital/clinic/physician's office medical records), if possible. The nature and location of all source documents will be identified to ensure that all sources of original data required to complete the eCRF are known to the sponsor and study-site personnel. If electronic records are maintained at the study site, the method of verification must be discussed with the study-site personnel.

If possible, given the current pandemic, direct access to source documents (medical records) must be allowed for the purpose of verifying that the recorded data are consistent with the original source data. Findings from this review will be discussed with the study-site personnel. The sponsor expects that, during monitoring visits, the relevant study-site personnel will be available, the source documents will be accessible, and a suitable environment will be provided for review of study-related documents. The monitor will meet with the investigator on a regular basis during the study to provide feedback on the study conduct.

In addition to on-site monitoring visits, remote contacts can occur. It is expected that during these remote contacts, study-site personnel will be available to provide an update on the progress of the study at the site.

Central monitoring will take place for data identified by the sponsor as requiring central review.

10.4.12. Audits

Representatives of the sponsor's clinical quality assurance department may conduct an audit remote and/or on-site (when feasible) at any time during or after completion of the study in compliance with regulatory guidelines and company policy. These audits will require access to all study records, including source documents, for inspection. Participant privacy must, however, be respected. The investigator and study-site personnel are responsible for being present and available for consultation during routinely scheduled study-site audit visits conducted by the sponsor or its designees.

Similar auditing procedures may also be conducted by agents of any regulatory body, either as part of a national GCP compliance program or to review the results of this study in support of a regulatory submission. The investigator should immediately notify the sponsor if he or she has been contacted by a regulatory agency concerning an upcoming inspection.

10.4.13. Record Retention

In compliance with the ICH/GCP guidelines, the investigator/institution will maintain all eCRF and all source documents that support the data collected from each participant, as well as all study documents as specified in ICH/GCP Section 8, Essential Documents for the Conduct of a Clinical Trial, and all study documents as specified by the applicable regulatory requirement(s). The investigator/institution will take measures to prevent accidental or premature destruction of these documents.

Essential documents must be retained until at least 2 years after the last approval of a marketing application in an ICH region and until there are no pending or contemplated marketing applications in an ICH region or until at least 2 years have elapsed since the formal discontinuation of clinical development of the investigational product. These documents will be retained for a longer period if required by the applicable regulatory requirements or by an agreement with the sponsor. It is the responsibility of the sponsor to inform the investigator/institution as to when these documents no longer need to be retained.

If the responsible investigator retires, relocates, or for other reasons withdraws from the responsibility of keeping the study records, custody must be transferred to a person who will accept the responsibility. The sponsor must be notified in writing of the name and address of the new custodian. Under no circumstance shall the investigator relocate or dispose of any study documents before having obtained written approval from the sponsor.

If it becomes necessary for the sponsor or the appropriate regulatory authority to review any documentation relating to this study, the investigator/institution must permit access to such reports.

10.4.14. Study and Site Start and Closure

First Act of Recruitment

The first site open is considered the first act of recruitment and it becomes the study start date.

Study/Site Termination

The sponsor reserves the right to close the study site or terminate the study at any time for any reason at the sole discretion of the sponsor. Study sites will be closed upon study completion. A study site is considered closed when all required documents and study supplies have been collected and a study-site closure visit has been performed.

The investigator may initiate study-site closure at any time, provided there is reasonable cause and sufficient notice is given in advance of the intended termination.

Reasons for the early closure of a study site by the sponsor or investigator may include but are not limited to:

- Failure of the investigator to comply with the protocol, the requirements of the IEC/IRB or local health authorities, the sponsor's procedures, or GCP guidelines
- Inadequate recruitment of participants by the investigator
- Discontinuation of further study intervention development

10.5. Appendix 5 : Adverse Events, Serious Adverse Events, Product Quality Complaints, and Other Safety Reporting: Definitions and Procedures for Recording, Evaluating, Follow-up, and Reporting

10.5.1. Adverse Event Definitions and Classifications

Adverse Event

An adverse event is any untoward medical occurrence in a clinical study participant administered a pharmaceutical (investigational or non-investigational) product. An adverse event does not necessarily have a causal relationship with the intervention. An adverse event can therefore be any unfavorable and unintended sign (including an abnormal finding), symptom, or disease temporally associated with the use of a medicinal (investigational or non-investigational) product, whether or not related to that medicinal (investigational or non-investigational) product. (Definition per International Conference on Harmonisation [ICH]²⁸)

This includes any occurrence that is new in onset or aggravated in severity or frequency from the baseline condition, or abnormal results of diagnostic procedures, including laboratory test abnormalities.

Note: The sponsor collects adverse events as of time of obtaining consent, as specified in Section 8.3.1, Time Period and Frequency for Collecting Adverse Events and Serious Adverse Events Information.

Serious Adverse Event

A serious adverse event based on ICH and EU Guidelines on Pharmacovigilance for Medicinal Products for Human Use is any untoward medical occurrence that at any dose:

- Results in death
- Is life-threatening
(The participant was at risk of death at the time of the event. It does not refer to an event that hypothetically might have caused death if it were more severe.)
- Requires inpatient hospitalization or prolongation of existing hospitalization
- Results in persistent or significant disability/incapacity
- Is a congenital anomaly/birth defect
- Is a suspected transmission of any infectious agent via a medicinal product
- Is Medically Important*

*Medical and scientific judgment should be exercised in deciding whether expedited reporting is also appropriate in other situations, such as important medical events that may not be immediately life threatening or result in death or hospitalization but may jeopardize the participant or may require intervention to prevent one of the other outcomes listed in the definition above. These should usually be considered serious.

If a serious and unexpected adverse event occurs for which there is evidence suggesting a causal relationship between the study intervention and the event (eg, death from anaphylaxis), the event must be reported as a serious and unexpected suspected adverse reaction even if it is a component of the study endpoint.

Unlisted (Unexpected) Adverse Event/Reference Safety Information

An adverse event is considered unlisted if the nature or severity is not consistent with the applicable product reference safety information. For sirukumab, the expectedness of an adverse event will be determined by whether or not it is listed in the IB. For SOC treatment with a marketing authorization, the expectedness of an adverse event will be determined by whether or not it is listed in the local product information.

10.5.2. Attribution Definitions

Assessment of Causality

The causal relationship to study intervention is determined by the Investigator. The following selection should be used to assess all adverse events (AE).

Related

There is a reasonable causal relationship between study intervention administration and the AE.

Not Related

There is not a reasonable causal relationship between study intervention administration and the AE.

The term "reasonable causal relationship" means there is evidence to support a causal relationship.

10.5.3. Severity Criteria

An assessment of severity grade will be made by the investigator using the general categorical descriptors outlined in the Microbiology and Infectious Diseases (DMID) toxicity table (see Section 10.8, [Appendix 8](#) DMID Table).

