9.4.6. Safety Analyses

All safety analyses will be made on the Safety Population and on participants with confirmed (a) critical and (b) severe or critical COVID-19 disease.

Adverse Events

The verbatim terms used in the eCRF by investigators to identify adverse events will be coded using the Medical Dictionary for Regulatory Activities (MedDRA). Any AE occurring at or after the initial administration of study intervention is considered to be treatment-emergent. All reported AEs will be included in the analysis. For each AE, the percentage of participants who experience at least 1 occurrence of the given event will be summarized by intervention group.

Summaries, listings, datasets, or participant narratives may be provided, as appropriate, for those participants who die, who discontinue intervention due to an AE, or who experience a grade 3 or 4 AE, a serious AE, or an adverse event of special interest (AEOI).

The incidence of participants with SAEs, the incidence of participants with grade 3 or 4 AEs, the incidence of participants with severe or life-threatening, bacterial, invasive fungal, viral or opportunistic infections (other than SARS-CoV-2), the incidence of grade 3 and 4 neutropenia and lymphocytopenia, and the incidence of increased ALT $\geq 3 \times$ ULN combined with increased bilirubin $> 2 \times$ ULN will be reported. Increase of ALT or AST combined with increase of bilirubin will be investigated by means of evaluation of drug-induced serious hepatotoxicity (eDISH) plots.

Clinical Laboratory Tests

Laboratory data will be summarized by type of laboratory test. The laboratory abnormalities will be determined per the criteria specified in the DMID Adult Toxicity Table (Section 10.8, Appendix 8) and in accordance with the normal ranges of the clinical laboratory if no gradings are available. Tables showing n and percent of participants with treatment-emergent worst toxicity grades (for tests with defined toxicity grades) and treatment-emergent worst abnormalities (for tests without defined toxicity grades) during treatment phase will be generated. A listing of participants with any laboratory results outside the reference ranges will be provided. A listing of participants with any markedly abnormal laboratory results will also be provided.

Electrocardiogram

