Hypercalcemia (correct for albumin)	10.6 - 11.5 mg/dL	11.6 - 12.5 mg/dL	12.6 - 13.5 mg/dL	> 13.5 mg/dL or abnormal calcium with life-threatening arrhythmia
Hypomagnesemia	1.4 - 1.2 mEq/ L	1.1 - 0.9 mEq/ L	0.8 - 0.6 mEq/ L	< 0.6 mEq/ L or abnormal magnesium with life-threatening arrhythmia
Hypophosphatemia	2.0 - 2.4 mg/dL	1.5 -1.9 mg/dL or replacement Rx required	1.0 -1.4 mg/dL intensive therapy or hospitalization required	< 1.0 mg/dL or abnormal phosphate with life-threatening arrhythmia
Hyperbilirubinemia (when accompanied by any increase in other liver function test)	1.1 - <1.25 x ULN	1.25 - <1.5 x ULN	1.5 – 1.75 x ULN	> 1.75 x ULN
Hyperbilirubinemia (when other liver function are in the normal range)	1.1 - <1.5 x ULN	1.5 - <2.0 x ULN	2.0 – 3.0 x ULN	> 3.0 x ULN
BUN	1.25 - 2.5 x ULN	2.6 - 5 x ULN	5.1 - 10 x ULN	> 10 x ULN
Hyperuricemia (uric acid)	7.5 – 10.0 mg/dL	10.1 – 12.0 mg/dL	12.1 – 15.0 mg/dL	>15.0 mg/dL
Creatinine	1.1 - 1.5 x ULN	1.6 - 3.0 x ULN	3.1 - 6 x ULN	>6 x ULN or dialysis required

ENZYMES				
	Grade 1	Grade 2	Grade 3	Grade 4
AST (SGOT)	1.1 - <2.0 x ULN	2.0 – <3.0 x ULN	3.0 – 8.0 x ULN	> 8 x ULN
ALT (SGPT)	1.1 - <2.0 x ULN	2.0 – <3.0 x ULN	3.0 – 8.0 x ULN	> 8 x ULN
GGT	1.1 - <2.0 x ULN	2.0 – <3.0 x ULN	3.0 – 8.0 x ULN	> 8 x ULN
Alkaline Phosphatase	1.1 - <2.0 x ULN	2.0 – <3.0 x ULN	3.0 – 8.0 x ULN	> 8 x ULN
Amylase	1.1 - 1.5 x ULN	1.6 - 2.0 x ULN	2.1 - 5.0 x ULN	> 5.1 x ULN
Lipase	1.1 - 1.5 x ULN	1.6 - 2.0 x ULN	2.1 - 5.0 x ULN	> 5.1 x ULN

URINALYSIS

	Grade 1	Grade 2	Grade 3	Grade 4
Proteinuria	1+ or 200 mg - 1 gm loss/day	2-3+ or 1- 2 gm loss/day	4+ or 2-3.5 gm loss/day	nephrotic syndrome or >3.5 gm loss/day
Hematuria	microscopic only <10 rbc/hpf	gross, no clots >10 rbc/hpf	gross, with or without clots, OR RBC casts	obstructive or required transfusion

CARDIOVASCULAR

	Grade 1	Grade 2	Grade 3	Grade 4
Cardiac Rhythm		asymptomatic, transient signs, no Rx required	recurrent/persistent; symptomatic Rx required	unstable dysrhythmia; hospitalization and treatment required
Hypertension	transient increase >20 mm/ Hg; no treatment	recurrent, chronic increase > 20mm/ Hg /treatment required	acute treatment required; outpatient treatment or hospitalization possible	end organ damage or hospitalization required

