Hypotension	transient orthostatic hypotension with heart rate increased by <20 beat/min or decreased by <10 mm Hg systolic BP, No treatment required	symptoms due to orthostatic hypotension or BP decreased by <20 mm Hg systolic; correctable with oral flu id treatment	requires IV fluids; no hospitalization required	mean arterial pressure <60mm/ Hg or end organ damage or shock; requires hospitalization and vasopressor treatment
Pericarditis	minimal effusion	mild/ moderate asymptomatic effusion, no treatment	symptomatic effusion; pain; EKG changes	tamponade; pericardiocentesis or surgery required
Hemorrhage, Blood Loss	microscopic/occult	mild, no transfusion	gross blood loss; 1-2 units transfused	massive blood loss; >3 units transfused

RESPIRATORY

	Grade 1	Grade 2	Grade 3	Grade 4
Cough	transient- no treatment	persistent cough; treatment responsive	Paroxysmal cough; uncontrolled with treatment	-----
Bronchospasm, Acute	transient; no treatment; 70% - 80% FEV1 of peak flow	requires treatment; normalizes with bronchodilator; FEV1 50% - 70% (of peak flow)	no normalization with bronchodilator; FEV1 25% - 50% of peak flow; or retractions present	cyanosis: FEV1 <25% of peak flow or intubation necessary
Dyspnea	dyspnea on exertion	dyspnea with normal activity	dyspnea at rest	dyspnea requiring oxygen therapy

GASTROINTESTINAL

	Grade 1	Grade 2	Grade 3	Grade 4
Nausea	mild or transient; maintains reasonable intake	moderate discomfort; intake decreased significantly; some activity limited	no significant intake; requires IV fluids	hospitalization required;
Vomiting	1 episode in 24 hours	2-5 episodes in 24 hours	>6 episodes in 24 hours or needing IV fluids	physiologic consequences requiring hospitalization or requiring parenteral nutrition
Constipation	requiring stool softener or dietary modification	requiring laxatives	obstipation requiring manual evacuation or enema	obstruction or toxic megacolon
Diarrhea	mild or transient; 3-4 loose stools/day or mild diarrhea last <1 week	moderate or persistent; 5-7 loose stools/day or diarrhea lasting >1 week	>7 loose stools/day or bloody diarrhea; or orthostatic hypotension or electrolyte imbalance or >2L IV fluids required	hypotensive shock or physiologic consequences requiring hospitalization
Oral Discomfort/Dysphagia	mild discomfort; no difficulty swallowing	some limits on eating/drinking	eating/talking very limited; unable to swallow solid foods	unable to drink fluids; requires IV fluids

NEUROLOGICAL				

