9.1.3 Analysis Methods

There will be no formal statistical testing for the AEs.

A summary table will be generated for the following attributes of AEs for 2 study phases (treatment phase, follow-up phase):

- any AE,
- serious AEs,
- AEs leading to death,
- AEs with grade ≥ 3 ,
- AEs with grade ≥ 3 and related to study drug,
- AEs related to study drug,
- AEs of special interest,
- AEs of special interest and related to study drug.

AE incidence tables will be generated showing the SOC-Med and PT separately in two phases (treatment and follow-up), in descending order of frequency in Sirukumab treatment arm. For each AE, the percentage of participants who experience at least 1 occurrence of the given event will be summarized. The tables will be provided for the following attributes:

- AEs by SOC-Med and PT,
- Serious AEs by SOC-Med and PT,
- AEs of special interest,
- AEs related to study drug,
- AEs with Grade ≥ 3 ,
- AEs leading to death.

Separate listings of participants with serious AE, AEs leading to death and AE ≥ 3 grade and AE related to study drug will be generated.

A table showing number of participants with SOC-Med of Infection and Infestation vs Lymphocytopenia Grade 3-4 during treatment phase will be generated.

Subgroup Analysis:

Tables for the following AE attributes will be generated by 2 subgroups: (Age: < 65 , ≥ 65 years, CRS score at baseline: ≤ 3 , ≤ 4 , 4, 5).

- Serious AEs,
- AEs of special interest, AEs related to study drug,
- AEs with Grade ≥ 3 ,
- AEs leading to death.

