ATTACHMENT 1. WHO GRADING SCALE VITAL SIGNS

The following abnormalities are defined for vital signs:

| Vital Signs parameter | | | |
|-----------------------|-----------|------------------------|-------------------------|
| Abnormality Code | Pulse | DBP* | SBP* |
| Abnormally low | < 45 bpm | ≤ 50 mmHg | ≤ 90 mmHg |
| Grade 1 or mild | - | > 90 mmHg - < 100 mmHg | > 140 mmHg - < 160 mmHg |
| Grade 2 or moderate | - | ≥100 mmHg - < 110 mmHg | ≥160 mmHg - < 180 mmHg |
| Grade 3 or severe | - | ≥ 110 mmHg | ≥ 180 mmHg |
| Abnormally high | ≥ 120 bpm | - | - |

* The classification of AEs related to hypotension and hypertension will be done according to the WHO grading scale

| Abnormality Code | Vital Signs parameter | |
|---|---|--|
| | Temperature (°C/°F) | Respiratory rate (breaths per minute) |
| Grade 1 or mild | > 38.0 - <= 38.6 °C or > 100.4 - <= 101.5 °F | 17-20 |
| Grade 2 or moderate | > 38.6 - <= 39.3 °C or > 101.5 - <= 102.7 °F | 21-25 |
| Grade 3 or severe | > 39.3 - <= 40.0 °C or > 102.7 - <= 104.0 °F | >25 |
| Grade 4 or potentially life-threatening | >40.0°C or > 104.0°F | |

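### Protocol 10.5.3 grades every AE on the DMID table, but a footnote in SAP Attachment 1 puts hypotension and hypertension AEs on a WHO blood-pressure scale with no graded level for low pressure

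*Protocol*

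**What the plan says.** **Protocol.** Section 10.5.3 covers all AEs: the "severity grade will be made by the investigator using the general categorical descriptors outlined in the Microbiology and Infectious Diseases (DMID) toxicity table". The cardiovascular rows of Appendix 8 define four grades each for hypotension and hypertension, and the upper grades turn mainly on treatment and consequence. Hypotension grade 3 is "requires IV fluids; no hospitalization required" and grade 4 is "mean arterial pressure <60mm/ Hg or end organ damage or shock; requires hospitalization and vasopressor treatment". Hypertension grade 3 is "acute treatment required; outpatient treatment or hospitalization possible"; grade 4 is organ damage or need for admission. Section 9.4.6 commits to reporting "the incidence of participants with grade 3 or 4 AEs".

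**SAP.** Section 9.1.2 lists an AE grade attribute running from 1 to 4 but names no scale. Section 9.1.3 uses that attribute in the summary table (including a row for "AEs with grade ≥ 3 and related to study drug"), a system-organ-class and preferred-term table, a listing, and subgroup tables by age and baseline CRS. Section 9.3.2 uses Attachment 1 to flag abnormal vital-sign measurements. The footnote to Attachment 1 goes further: "The classification of AEs related to hypotension and hypertension will be done according to the WHO grading scale". The only low-pressure row in that attachment reads "Abnormally low | < 45 bpm | ≤ 50 mmHg | ≤ 90 mmHg" (pulse, diastolic, systolic) and has no grade. High pressure has grades 1 to 3, set by mmHg alone.

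**The concern.** Two rules cover the same events and give different answers. The footnote is hard to dismiss as a restatement of the vital-signs rule: SAP 9.3.2 already covers measured values, and what the footnote adds is AEs. It is also the only place where the SAP names a scale for AE severity, since DMID is invoked there only for laboratory tests (SAP 4.2 and 9.2.2). A programmer looking in the SAP for the source of AE grade would find WHO for these two event types and nothing for the rest.

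The grade 3-or-higher comparison is a stated safety output, and blood-pressure events matter for this drug: Protocol Table 2 lists both hypotension and hypertension among the hypersensitivity reactions seen with monoclonal antibodies. Severe hypotension could be left out of that comparison because of the choice of scale and not because of anything observed in a participant.

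**Working it through.** The plan gives no figure to reproduce, so the check sets the two scales side by side.

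**Inputs.** DMID rows from Protocol Appendix 8. WHO limits from SAP Attachment 1: low is systolic ≤ 90 or diastolic ≤ 50, ungraded; grade 1 is systolic above 140 to below 160 or diastolic above 90 to below 100; grade 2 is systolic 160 to below 180 or diastolic 100 to below 110; grade 3 is systolic ≥ 180 or diastolic ≥ 110. Two assumptions are mine: mean arterial pressure (MAP) = (systolic + 2 × diastolic)/3, because the documents give no formula, and the worse of the systolic and diastolic codes counts.

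**Step 1: low pressure.**

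| Reading | MAP | DMID grade 4 MAP criterion (< 60) | WHO code |
|---|---|---|---|
| 90/60 | (90 + 120)/3 = 70.0 | no | low, ungraded |
| 90/50 | (90 + 100)/3 = 63.3 | no | low, ungraded |
| 80/45 | (80 + 90)/3 = 56.7 | yes | low, ungraded |
| 100/39 | (100 + 78)/3 = 59.3 | yes | low, ungraded |
| 60/30 | (60 + 60)/3 = 40.0 | yes | low, ungraded |

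The WHO code does not separate 90/60 from 60/30. The result is general: a reading outside the low code has systolic above 90 and diastolic above 50, so its MAP exceeds (90 + 100)/3 = 63.3. Every reading with MAP below 60 therefore falls in the ungraded code, and no low pressure can produce a WHO grade of 3 or more.

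**Step 2: treated hypotension.** A participant in shock whose pressure is held at 100/60 by vasopressors has MAP (100 + 120)/3 = 73.3 and receives no WHO code at all. DMID grade 4 can still apply, through its shock and organ-damage criteria.

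**Step 3: high pressure.**
- 170/105 needing acute treatment: DMID grade 3, WHO grade 2. It leaves a grade 3-or-higher table.
- 185/112, transient and untreated, recorded as an AE: DMID grade 1, WHO grade 3. It enters the table.
- DMID grade 4 hypertension: WHO grade 3 at most, and lower if the reading is below 180 systolic and 110 diastolic.

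**Step 4: effect on the tables.**

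| Source of AE grade | Hypotension AEs at grade 3 or higher | Hypertension AEs at grade 3 or higher |
|---|---|---|
| Investigator's DMID grade | as recorded | as recorded |
| WHO scale, per the footnote | none possible | can rise or fall |

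**Step 5: number affected.** This needs the rate of AEs recorded as hypotension or hypertension and the share of those participants with no other grade 3-or-higher AE. The documents give neither, so no count or percentage follows.

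**The case against.** The strongest reply is that the footnote was never meant to touch AE grade. It speaks of classification, sits under a vital-signs table, and belongs to an attachment whose stated use in SAP 9.3.2 is measured abnormalities. The section that governs the AE tables, SAP 9.1, keeps grades 1 to 4, contains no rule for replacing an investigator's grade and no rule linking an AE to a particular reading. SAP Section 1 says the plan is to be read together with the protocol, so the DMID grade can stand. This has force: the SAP does not say that the recorded grade is overridden, and the loss is conditional on that reading. It does not remove the conflict, because the footnote still states a rule for AEs that differs from Protocol 10.5.3. The clause in Appendix 8 that lets protocol-specific criteria supersede DMID does not help either, since the protocol contains none for blood pressure.

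A reader might infer that shock from infection would vanish from the safety report. The documents do not support that. Protocol 10.5.5 asks for the diagnosis where signs share a cause, so septic shock would normally be recorded as such and keep its grade. Serious infections are an AE of special interest with their own table, and severe or life-threatening infections are a named secondary safety endpoint. Serious AEs and AEs leading to death are also tabulated separately.

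A reader might also infer that stray pressure readings would be counted as severe AEs. The footnote classifies AEs; it does not create them. Under Protocol 8.2.2 an abnormal vital sign is documented as an AE if it is serious, possibly drug-related or an event of interest, so many transient high readings would never be AEs. Sparse measurement is not the problem: vital signs are taken at least four times a day in the ICU, and SAP 9.3.2 uses all of them.

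**Conclusion.** Wrong as written, as a conflict between protocol and SAP; minor severity. The protocol prescribes DMID for all AEs, and the SAP footnote prescribes WHO for AEs related to hypotension and hypertension. The WHO scale cannot express severe hypotension and can move hypertension AEs in either direction.

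The consequence is conditional. If the footnote sets AE grade, no AE recorded as hypotension can appear in any grade 3-or-higher output of SAP 9.1.3. If the DMID grade is kept, every table is unchanged. Which of the two would happen cannot be read from the documents.

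The reach is limited. The incidence of grade 3 or 4 AEs is descriptive, is not among the listed secondary endpoints, and AEs are not formally tested. Efficacy and the laboratory-based grade 3 and 4 neutropenia and lymphocytopenia endpoints are untouched. Any percentage-point understatement would rest on assumed event rates, so none is given. The low-pressure result depends on the usual MAP formula only for the MAP criterion; the absence of a graded low level is plain from Attachment 1.

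**What to change.** 1. Delete the footnote in SAP Attachment 1, or reword it so that it covers only the measured vital-sign abnormalities of SAP 9.3.
2. Add one sentence to SAP 9.1.2: the AE grade used in all AE tables and listings, including for hypotension and hypertension, is the investigator's DMID grade recorded under Protocol 10.5.3.

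The WHO limits stay in use for the vital-sign tables. The cost is one footnote and one sentence, with no new data collection and no protocol amendment. The change concerns reporting only and should be made before the database lock for the primary analysis.
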